7.2.3 Overlapping Toxicities

Nausea, vomiting, anorexia and diarrhea are frequent AEs that could be attributed to both drugs independently. The temporal course may help to determine the attribution to a particular drug. If both drugs are considered to be the cause of these AEs, the recommendations are to follow dose modifications for BBI608 and temozolomide, as indicated above.

7.2.4 Start of a new Cycle

Drug(s) will be resumed once all toxicities have recovered to Grade <2.

7.3 Treatment Compliance

A patient is considered compliant with the study protocol when he or she takes at least 80% of both the assigned study medication and TMZ. Treatment compliance will be monitored via Patient Diary in order to verify the Per Protocol patient population.

BBI608 and TMZ compliance will be calculated using the following equation:

$$\% \text{ Compliance} = \frac{\text{Number of capsules actually ingested in a given time period}}{\text{Number of capsules that should have been ingested per dose level}} \times 100$$

7.4 Blinding

This is an open label study. Neither the patient nor the investigator and site staff will be blinded to the treatment administered.

7.5 Prior Treatment

Reasonable efforts will be made to determine all relevant prior treatments received by the patient. All relevant information must be recorded on the appropriate patient's Case Report Form (CRF). All surgical procedure history, prior chemotherapy, and radiation therapy must be recorded on the appropriate CRF.

7.6 Concomitant Medication

7.6.1 Permitted Treatment

All information regarding concomitant treatments (medications or procedures) must be recorded on the patient's CRF (including the name of the medication or procedure and duration of treatment).

Concurrent corticosteroid administration is permitted as specified in the inclusion criteria. Any corticosteroid administration must be recorded on the patient's CRF. Steroid dosing will be adjusted as clinically appropriate during therapy.

Palliative and supportive care for disease-related symptoms will be offered to all patients in this study.

BBI608 was shown *in vitro* to inhibit individual CYP P450 isoforms 1A2, 2D6, 2C19, 3A4, and 2C9 with IC₅₀'s of 0.25 μM, 0.25 μM, 2.5 μM, 5 μM, and 0.5 μM respectively, under serum-free conditions. Since BBI608 has shown the ability to inhibit these CYP P450 isoforms *in vitro*, concomitant use of agents that are substrates of these CYP P450 enzymes should be used only if deemed medically necessary by the primary investigator. Examples of commonly prescribed agents that are metabolized by these CYP P450 enzymes are:

- NSAIDS: such as ibuprofen, naproxen
- Proton pump inhibitors: such as lansoprazole, omeprazole
- Oral hypoglycemic medications: sulfonylureas
- Beta-blockers: metoprolol, carvedilol
- Calcium channel blockers: amlodipine, diltiazem, nifedipine, verapamil
- Antidepressants: paroxetine, imipramine, amitriptyline
- Anti-epileptics: such as phenytoin, phenobarbitone
- Anti-psychotics: such as haloperidol, risperidone
- Antibiotics: such as clarithromycin, erythromycin

HMG CoA reductase inhibitor: atorvastatin, lovastatin, simvastatin
Anesthetics: such as halothane, enflurane;
HIV antivirals: such as saquinavir, indinavir, ritonavir
Immunomodulators (immunosuppressives): such as cyclosporine, tacrolimus
Steroids: such as hydrocortisone, estrodiol

BBI608 is metabolized by the CYP P450 isoform 1A2. Therefore, concomitant use of drugs that inhibit or induce CYP1A2 should be avoided unless deemed medically necessary by the primary investigator.

Known drugs that inhibit CYP 1A2 include ciprofloxacin and other fluoroquinolones, Fluvoxamine Verapamil, amiodarone, interferon, methoxsalen, enoxacin, mexiletine, and ticlopidine.

Several common anti-epileptic drugs are known to induce CYP1A2 including carbamazepine, phenobarbital and phenytoin. These enzyme-inducing anti-epileptics (EIAEDs) should be avoided with concomitant BBI608 treatment, and a non-AEID alternative anti-convulsant should be used instead.

Of note, no clinically apparent drug-drug interactions occurred during phase I or phase Ib/II studies conducted with BBI608 thus far.

In addition, the following treatments are allowed:

- Standard therapies for concurrent medical conditions
- Epoetin alfa (Epogen[®], Procrit[®])
- Hematopoietic growth factors, including filgrastim (Neupogen[®]), or other granulocyte colony stimulating factors (G-CSF), are permitted following documented and clinically significant neutropenia after the patient has completed at least one cycle of treatment with BBI608
- Prophylactic antiemetics may be administered according to standard practice
- Low dose corticosteroids used as an antiemetic regimen
- Megestrol acetate (Megace[®])

7.6.2 Budesonide - Interaction with CYP3A4 inhibitors

Concomitant oral administration of ketoconazole (a known inhibitor of CYP3A4 activity in the liver and in the intestinal mucosa) caused an eight-fold increase of the systemic exposure to oral budesonide. If treatment with inhibitors of CYP3A4 activity (such as ketoconazole, itraconazole, ritonavir, indinavir, saquinavir, erythromycin) is indicated, discontinuation of budesonide should be considered. After extensive intake of grapefruit juice (which inhibits CYP3A4 activity predominantly in the intestinal mucosa), the systemic exposure for oral budesonide increased about two times. Ingestion of grapefruit or grapefruit juice should be avoided in connection with budesonide administration.

7.6.3 Prohibited Treatment

- Any concurrent chemotherapy, radiotherapy, hormonal therapy, or immunotherapy; palliative radiotherapy for non-target lesions may be permitted in certain cases as decided by the principal investigator and sponsor
- Other investigational agents
- CYP1A enzyme-inducing antiepileptic drugs (including phenobarbital, phenytoin, and carbamazepine)
- Immunosuppressive therapies, including systemic corticosteroids (except when used intermittently, such as in an antiemetic regimen, or when used for GBM)

8 SAFETY ASSESSMENTS

8.1 Adverse Events

8.1.1 Assessments

The Investigator is responsible for monitoring the safety of patients who have enrolled in the study. All AEs considered to be related to BBI608 occurring after any administration of the study drug will be followed until the event resolves. AEs will be evaluated using the National Cancer Institute (NCI) CTCAE, Version 4.0.

Investigators are required to document all AEs occurring during the clinical trial, commencing with study enrollment and including the protocol-defined post-treatment follow-up period (21 Code of Federal Regulations [CFR] §312.64[b]) on designated CRF pages. It is also important to record all AEs that result in permanent discontinuation of the investigational product being studied, whether serious or non-serious.

Serious adverse events (SAEs), as defined below, must be reported to Boston Biomedical or its representative within 24 hours of knowledge of their occurrence.

8.1.2 Definitions

An adverse event (AE) is defined as any untoward medical occurrence in a patient or clinical investigation subject that does not necessarily have a causal relationship with this treatment. An AE can therefore be any unfavorable and unintended sign (including an abnormal laboratory finding), symptom, or disease temporally associated with the use of a medicinal (investigational) product, whether or not considered related to the medicinal product.

Laboratory data are to be collected as stipulated in this protocol, and toxicity trends will be analyzed utilizing objective toxicity criteria. Clinical syndromes associated with laboratory abnormalities are to be recorded as appropriate (e.g., diabetes mellitus instead of hyperglycemia).

Progression of disease is considered an efficacy outcome parameter and should not be captured as an AE. A non-serious AE is any untoward medical occurrence that does not meet any of the criteria for SAEs as defined below.

Patients should be instructed to report any AE that they experience to the Investigator. Investigators should assess the patient for AEs at each visit. AEs occurring during the clinical trial and the follow-up period should be recorded on the appropriate AE CRF. To

capture the most potentially relevant safety information during a clinical trial, it is important that investigators record accurate AE terms on CRFs.

Wherever possible, a specific disease or syndrome rather than individual associated signs and symptoms should be identified by the investigator and recorded on the CRF. However, if an observed or reported sign or symptom is not considered a component of a specific disease or syndrome by the investigator, it should be recorded as a separate AE on the CRF.

8.2 Serious Adverse Events

8.2.1 Definitions

A serious adverse event (SAE) is any adverse event occurring at any dose that results in any of the following outcomes:

- Death
- A life-threatening adverse drug experience
- Inpatient hospitalization or prolongation of existing hospitalization
- A persistent or significant disability/incapacity
- A congenital anomaly/birth defect

Important medical events may be considered an SAE based upon appropriate medical judgment.

Under this protocol, scheduled hospitalizations or elective surgical/medical procedures or elective hospitalization will not be considered SAEs. Prolongation of a scheduled hospitalization can be considered an SAE. Complications associated with scheduled procedures are considered an AE.

8.2.2 Reporting Serious Adverse Events

Any SAE, including death, due to any cause that occurs during this investigation, whether or not related to the administration of study drug, must be reported to the Sponsor immediately (not to exceed 24 hours) by telephone, secured email or facsimile. The reaction must be completely described on the CRF and SAE report form.

Primary Medical Monitor Contact information:
[name] [name] [contact] [name] [contact] Email: [contact] Emergency Number: [contact]

9 ASSESSMENT OF ANTI-TUMOR ACTIVITY

The following definitions and criteria (from Response Assessment in Neuro-Oncology [RANO Wen et al., 2010] Working Group criteria) should be used for the baseline evaluations of existing disease, and for the ongoing evaluation of tumor responses.

Measurable disease - presence of at least one measurable lesion.

Measurable lesions - lesions that are bidimensionally contrast-enhancing with clearly defined margins by CT or MRI scan, with two perpendicular diameters of at least 10 mm, visible on two or more axial slices that are preferably, at most, 5 mm apart with 0-mm skip. The size of a measurable lesion at baseline should be two times the slice thickness.

Non-measurable lesions - all other lesions, including small lesions (longest perpendicular diameters < 10 mm), unidimensionally measurable lesions, or masses with margins not clearly defined.

- All measurements should be taken and recorded in metric notation, using a ruler or calipers.
- The same method of assessment and the same technique should be used to characterize each identified and reported lesion at baseline and during follow-up.
- Tumor surrounding a cyst or a surgical cavity should be considered non-measurable unless there is a nodular component measuring ≥ 10 mm in diameter.

9.1 Method of Measurement

- MRI (T1-weighted contrast-enhanced images as well as T2-weighted/FLAIR images) is the best currently available and reproducible method to measure target lesions selected for response assessment. Conventional MRI should be performed with cuts of 5 mm or less in slice thickness contiguously.
- CT scan with contrast enhancement may be used for patients with MRI non-compatible devices.
- All imaging methods should be performed according to institutional standards with each patient having consistency of methods beginning from baseline through the course of the study.
- Ideally patients should be imaged on the same MRI or CT (for patients with MRI non-compatible devices), or at least with the same magnet strength, for the duration of the study to reduce difficulties in interpretation of images.

9.2 Baseline Documentation of “Target” and “Non-Target” Lesions

- If there are multiple contrast-enhancing lesions, a minimum of two lesions up to a maximum of five lesions total should be identified as *target lesions* and recorded and measured at baseline.

- Target lesions should be selected on the basis of their size (lesions with the longest diameter) and their suitability for accurate repeated measurements (either by imaging techniques or clinical assessments).
- Occasionally, the largest lesions may not allow reproducible repeated measurements, and the next largest lesions that can be measured reproducibly should be selected.
- A sum of the products of the perpendicular longest diameters (LD) for *all target lesions* will be calculated and reported as the baseline sum LD. The baseline sum LD will be used as the reference by which to characterize the objective tumor response.
- Patients with multiple lesions of which only 1 or 2 are increasing in size, the enlarging lesions should be considered the *target lesions* for evaluation of response. The other lesions will be considered *non-target lesions* and should also be recorded.
- The cystic or surgical cavity should not be measured for response determination.
- All other lesions (or sites of disease) should be identified as *non-target lesions* and should also be recorded at baseline. Measurements of these lesions are not required, but the presence or absence of each should be noted throughout follow-up.

9.3 Response Criteria

Radiographic response should be determined in comparison to the tumor measurement obtained at pretreatment baseline for determination of response, and the smallest tumor measurement at either pretreatment baseline or after initiation of therapy for determination of progression. For patients in Arm A who undergo surgical resection, the post-operative baseline scan (performed 48-72 hours after surgery) should be used for response assessment.

Response criteria are outlined below. In the event that the radiographic changes are equivocal and it is unclear whether the patient is stable or has developed progressive disease, it is permissible to continue treatment and observe the patient closely, for example at 4-week intervals. If subsequent imaging studies demonstrate that progression has occurred, the date of progression should be the date of the scan at which progression was first suspected.

Complete Response*

Requires ALL of the following:

1. Complete disappearance of all enhancing measurable and non-measurable disease sustained for at least 4 weeks.
2. No new lesions.
3. Stable or improved non-enhancing (T2/FLAIR) lesions.
4. Patients must be off corticosteroids (or on physiologic replacement doses only).
5. Patients must be stable or improved clinically.[#]

Partial Response*

Requires ALL of the following:

1. Greater than or equal to 50% decrease compared to baseline in the sum of products of perpendicular diameters of all measurable enhancing lesions sustained for at least 4 weeks.
2. No progression of non-measurable disease.
3. No new lesions.
4. Stable or improved non-enhancing (T2/FLAIR) lesions on same or lower dose of corticosteroids compared to baseline scan.
5. The corticosteroid dose at the time of the scan evaluation should be no greater than the dose at time of baseline scan.
6. Patients must be stable or improved clinically.#

Stable Disease

Requires ALL of the following:

1. Does not qualify for complete response, partial response, or progression.
2. Stable non-enhancing (T2/FLAIR) lesions on same or lower dose of corticosteroids compared to baseline scan. IN the event that the corticosteroid dose was increased for new symptoms and signs without confirmation of disease progression on neuroimaging, and subsequent follow-up imaging shows that this increase in corticosteroids was required because of disease progression, the last scan considered to show stable disease will be the scan obtained when the corticosteroid use was equivalent to the baseline dose.
3. Patients must be stable clinically.#

Progressive Disease

Defined by ANY of the following:

1. Greater than 25% increase in the sum of the products of perpendicular diameters of enhancing lesions compared to the smallest tumor measurement obtained either at baseline (if no decrease) or best response, on stable or increasing doses of corticosteroids.**
2. Significant increase in T2/FLAIR non-enhancing lesion on stable or increasing doses of corticosteroids compared to baseline scan or best response following initiation of therapy,* not due to co-morbid events (e.g. radiation therapy, demyelination, ischemic injury, infection, seizures, post-operative changes, or other treatment effects).
3. Any new lesion.
4. Clear clinical deterioration not attributable to other causes apart from the tumor (e.g. seizures, medication side effects, complications of therapy, cerebrovascular events, infection, etc.) or changes in corticosteroid dose.#
5. Failure to return for evaluation due to death or deteriorating condition.
6. Unequivocal progression of non-measurable disease.

*Patients with non-measurable disease only cannot have a complete or partial response. The best response possible is stable disease.

**Stable doses of corticosteroids include patients not on corticosteroids.

#Clinical status will be assessed via ECOG Performance Score.

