3.1.2. Phase II

Progression free survival (PFS) at 6 months of BBI608 administered in combination with TMZ: is defined as the proportion of patients who have survived without objective disease progression per RANO criteria for at least 6 months after enrollment.

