10.2. Appendix 1.2 Censoring for Time to Event Data

Table 4 summarizes the censoring rules for the PFS analysis and displays censoring hierarchy for this study. Table 5 shows the general reasons for PFS censoring and where the censoring hierarchy in **Table 4** came from.

Table 4 Event or Censor Time for PFS and Censoring Hierarchy

Censoring Hierarchy	Situation	Date of Event or Censor	Event / Censor
1	No baseline radiological tumor assessment available	Date of First Dose	Censored
2	New anticancer treatment started and no tumor progression	Date of previous adequate radiological assessment immediately prior to start of new therapy or Date of first dose, whichever comes later	Censored
3	Tumor progression (per RANO) documented after 2 scan intervals following previous adequate radiological tumor assessment	Date of previous adequate radiological assessment or Date of first dose, whichever comes later	Censored
4, 5	No tumor progression (per RANO) and subject lost to follow-up or withdrawal of consent	Date of last adequate radiological Assessment or Date of first dose, whichever comes later	Censored
6	No post baseline radiological tumor assessment available and no death reported within 2 scan intervals following the date of the first dose of study drug (BBI608)	Date of First Dose	Censored
7	No post baseline radiological tumor assessment available but death reported within 2 scan intervals following the date of the first dose of study drug (BBI608)	Date of Death	Event

	No tumor progression (per RANO) and no death reported within 2 scan intervals following last adequate radiological tumor assessment	Date of last adequate radiological tumor assessment or Date of first dose, whichever comes later	Censored
	No tumor progression (per RANO) but death reported within 2 scan intervals following last adequate radiological tumor assessment	Date of death	Event
	Tumor progression (per RANO) documented within 2 scan intervals following previous adequate radiological tumor assessment	Earliest of the target, non-target and new tumor assessment dates	Event

Notes: (1) Symptomatic deteriorations (i.e. symptomatic progressions, which are not radiographically confirmed) will not be considered as progressions.

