(2) If target, non-target and new lesion assessments have different dates within a visit, then the earliest of those dates will be considered as the date of the tumor assessment if the assessment for that visit is progressive disease (PD); otherwise the latest date will be used.

(3) Adequate radiographical tumor assessment refers to an assessment with overall response of CR, PR, SD or PD.

(4) Comparing date of last tumor assessment to date of first dose is necessary if the last tumor assessment is baseline assessment

Table 5 PFS Censoring Reasons and Hierarchy

Hierarchy	Condition	Censoring Reason
1	No adequate baseline assessment	No adequate baseline assessment
2	Start of new anti-cancer therapy before event.	Start of new anti-cancer therapy
3	Event more than 2 weeks from last adequate post-baseline tumor assessment/start date	Event after missing assessments ^a
4	No event and [withdrawal of consent date \geq start date OR End of study (EOS) = Subject refused further FU]	Withdrawal of consent
5	No event and lost to follow-up in any disposition page	Lost to follow-up

6	No event and [EOS present OR disposition page for any EPOCH after screening says patient will not continue into any subsequent phase of the study] and no adequate post-baseline tumor assessment	No adequate post-baseline tumor assessment
7	No event and none of the conditions in the prior hierarchy are met	Ongoing without an event

For OS, patients last known to be alive are censored at date of last contact.

Date of Last Contact

The date of last contact will be derived for patients not known to have died at the analysis data cutoff date using the latest complete date (non-imputed) among the following:

- All patient assessment dates (e.g., blood draws [laboratory, PK], vital signs, performance status, ECG, tumor assessments, concomitant radiation, surgery)
- Start and end dates of follow-up anti-cancer therapies
- AE start and end dates
- Last date of contact where “Subject Remains in Follow-up” collected on the “Survival Follow-up” eCRF (do not use date of survival follow-up assessment unless status is alive)
- Study drug start and end dates
- Date of discontinuation on disposition eCRF pages (do not use if reason for discontinuation is lost to follow-up or death).

Note:

1. This list is not all inclusive and should be agreed upon by the study team according to the data collected in the CRF

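### Protocol 9.3 back-dates confirmed progression to the first suspicious scan; the SAP's dating rule does not, so an equivocal week-24 scan in Arm B can drop out of the PFS-6 failures

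*Protocol*

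**What the plan says.** Protocol 9.3 covers the case where imaging changes are equivocal. Treatment may continue, and the site may "observe the patient closely, for example at 4-week intervals". If later imaging shows that progression has occurred, "the date of progression should be the date of the scan at which progression was first suspected".

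The SAP restates the RANO criteria in section 10.1 and then sets its own dating rule in section 10.2. It does not carry the back-dating sentence in either place.

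- **Table 4, last row.** The situation is "Tumor progression (per RANO) documented within 2 scan intervals following previous adequate radiological tumor assessment", and the event date is the "Earliest of the target, non-target and new tumor assessment dates".
- **Note 2 to Table 4.** When lesion assessments within one visit carry different dates, "then the earliest of those dates will be considered as the date of the tumor assessment if the assessment for that visit" is PD.
- **Table 5, hierarchy 3.** The condition for censoring is "Event more than 2 weeks from last adequate post-baseline tumor assessment/start date". Table 4 uses two scan intervals for the same purpose.

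The primary endpoint (SAP 3.1.2) is the proportion who have "survived without objective disease progression per RANO criteria for at least 6 months after enrollment". SAP 8.2.2.2 estimates it by Kaplan-Meier with an 80% interval on the log cumulative hazard scale, counting time from first dose in months of 30.4375 days.

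**The concern.** The two documents give different event dates for the same patient if the equivocal visit keeps a rating of SD or NE. The protocol uses the equivocal scan; the SAP uses the later visit rated PD.

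The Arm B schedule places this difference on the 6-month landmark. The week-24 scan falls shortly before six months, and a repeat four weeks later falls shortly after. The SAP rule can only delay these events, so any effect on PFS-6 is upward. The trial is open-label and the SAP's response data are investigator assessments, so whether a scan is called equivocal is a site judgement.

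**Working it through.** **Inputs.** Arm B scans are every 8 weeks from Cycle 1 Day 1, ±7 days (Protocol Appendix B), and Cycle 1 Day 1 is the first dose (Protocol 5.4.1). The repeat is taken at 28 days, the protocol's own example. Time in months is (days after first dose + 1)/30.4375 (SAP 8.2.2.2), so six months is 6 × 30.4375 = 182.6 days. The design has n = 30 per arm and a projected PFS-6 of 20% (Protocol 10.2).

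**The plan's own figure.** The Clopper-Pearson two-sided 80% interval for 6/30 is 10.9% to 32.5%. The stated lower bound above 10% is reproduced.

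**Arm B dates.**

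| Week-24 scan | Protocol date | Visit rated PD, 28 days later |
|---|---|---|
| 7 days early (day 161) | 162/30.4375 = 5.32 | 190/30.4375 = 6.24 |
| On time (day 168) | 169/30.4375 = 5.55 | 197/30.4375 = 6.47 |
| 7 days late (day 175) | 176/30.4375 = 5.78 | 204/30.4375 = 6.70 |

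The classification changes anywhere in the window. With a 28-day repeat, it changes for any first-suspected scan 154 to 181 days after first dose. An on-time week-16 equivocal scan does not matter for PFS-6: its SAP date would be 4.63 months after a 4-week repeat and 5.55 months after 8 weeks.

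**Arm A.** Run-in (5 to 9 days) plus the interval from surgery (15 to 28 days) puts Cycle 1 Day 1 at 20 to 37 days after first dose. An on-time week-24 scan is then at 189/30.4375 = 6.21 to 206/30.4375 = 6.77 months, beyond the landmark under either rule. The exceptions are at the edges: a scan 7 days early with the shortest lead (5.98 months), or a week-16 scan 7 days late with a lead of 35 to 37 days, repeated at 6.01 to 6.08 months.

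**What the SAP does with the Arm B patient.**

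- Week-24 scan rated SD: PD comes 4 weeks after an adequate assessment, inside Table 4's 2 × 8 = 16 weeks. It is an event at 6.47 months, so a PFS-6 success.
- Week-24 scan rated NE: the last adequate scan is week 16, and PD 12 weeks later is still inside 16 weeks. Same result under Table 4.
- Table 5 read literally, with an adequate week-24 scan: 4 weeks exceeds 2 weeks, so the patient is censored at about 5.55 months. With 23 earlier events and the other patients handled as before, the Kaplan-Meier estimate is 1 − 23/30 = 23.3%, the same as under Table 4.

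**Effect of one patient.** PFS-6 moves from 6/30 = 20.0% to 7/30 = 23.3%, or +3.3 points. The exact 80% lower bound moves from 10.9% to 13.5%. For the SAP's interval with no early censoring, the lower limit is S^exp(1.2816 θ), where θ = √[(1 − S)/(nS)]/|ln S|:

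- S = 6/30: θ = 0.3651/1.6094 = 0.2269, lower limit 11.6%.
- S = 7/30: θ = 0.3309/1.4553 = 0.2274, lower limit 14.3%.

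**Illustration of frequency (assumed inputs).** Assume exponential PFS with 20% at six months, every event found by scan, and a 28-day repeat for each equivocal read. Then S(112) = 0.2^(112/182.625) = 0.3727 and S(168) = 0.2^(168/182.625) = 0.2275. A share 0.3727 − 0.2275 = 0.145 of patients, about 4.4 of 30, is first detected at week 24. If 10%, 20% or 30% of those reads are equivocal, about 0.4, 0.9 or 1.3 patients change class. A simulation of 400,000 patients with the ±7-day window gave PFS-6 of 22.7% back-dated, rising to 24.2%, 25.6% and 27.1%.

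**The case against.** The best defence is that the SAP is silent on this case and does not contradict the protocol. Note 2 deals with different lesion dates inside one visit and does not mention equivocal scans. Progression in the SAP is per RANO, and the protocol is its first reference. If a site applies 9.3 by recording the first-suspected visit as PD, Table 4 and note 2 return the protocol's date. This stands as a condition: the CRF is not available, and no text says which rating the earlier visit keeps. It does not remove the point, because no text tells the site to re-rate that visit. SAP 10.1 also copies the retrospective corticosteroid rule for stable disease while leaving this one out.

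A reader might infer that every such patient is counted as a success and that the primary result is therefore inflated. The documents do not support this. Table 5 read literally censors the patient instead. That reading can hardly be intended, since successive scheduled scans are 8 weeks apart and all exceed two weeks, but the conflict is on the page. Nor do the documents say how often scans are equivocal. Deaths are dated at death and do not shift, and the four-week repeat is only an example.

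A reader might also infer that one reclassified patient could decide the trial. SAP 4.1 states that there is no hypothesis testing, and the 10% bound is a precision statement with no go/no-go rule attached. A change of 3.3 points is small beside an exact 80% interval of 10.9% to 32.5%.

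**Conclusion.** The point holds in conditional form. The SAP lacks the Protocol 9.3 dating rule, and its own rule, followed as written, loses a protocol-defined PFS-6 failure when an Arm B week-24 scan is equivocal, keeps its SD or NE rating, and is followed by PD about four weeks later. The failure is lost whether Table 4 or the literal Table 5 governs. It biases an estimate upward, by about 3.3 points per patient at n = 30; no error rate is involved.

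The range of 24.2% to 27.1% against 22.7% is an upper-end illustration. It rests on assumed equivocal rates of 10% to 30%, all events scan-detected, a fixed 28-day repeat and exponential PFS.

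The result does not depend much on the time origin. The SAP counts from first dose, and Protocol 11.2 places enrollment there too. Protocol 5.1 could place it earlier. With an assumed lead of up to 10 days, an on-time week-24 scan is at most (168 + 10 + 1)/30.4375 = 5.88 months, still a failure; only a late scan with the full lead passes six months (6.11).

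**What to change.** - In SAP 10.2, Table 4 and note 2, add that when an equivocal scan is followed by PD, the event date is the scan at which progression was first suspected, as in Protocol 9.3. Keep the current rule otherwise.
- Reconcile Table 5's two-week limit with Table 4's two scan intervals, so that these events are not censored.
- Report PFS-6 under the current SAP dating as a pre-specified sensitivity analysis. SAP 10.1 now makes PFS sensitivity analyses optional.

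**Cost.** The wording change is small, and PFS-6 may be slightly lower. The real cost is data. If the first-suspected date is not on the CRF, it must be queried retrospectively in an open-label trial whose follow-up the sponsor ended after 29 June 2018 (SAP 8.1.1). When progression was suspected is a judgement that knowledge of the outcome can colour, so take the date from scan reports or visit records made at the time.
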